7. STUDY POPULATION

[REDACTED]
[REDACTED]
[REDACTED]
[REDACTED]
[REDACTED]
[REDACTED]

This study will include only subjects who meet all the study inclusion and none of the exclusion criteria [REDACTED] All subjects who qualify will be

offered enrollment in the study. Any questions regarding patient eligibility are to be discussed with JJSV prior to subject enrollment.

7.1 INCLUSION CRITERIA

- [REDACTED]

Inclusion Criteria [REDACTED] (all criteria apply to both eyes):

- 1) Age \geq 18 years old.
- 2) Subjects with myopia or hyperopia with or without astigmatism (including mixed astigmatism) eligible for commercial LASIK treatment.
- 3) A residual anticipated stromal bed thickness of at least 250 microns based on preoperative central corneal pachymetry minus the maximum treatment depth to be ablated plus the intended flap thickness.
- 4) Distance Best Spectacle Corrected Visual Acuity (BSCVA) of 20/20 or better
- 5) Distance Uncorrected Visual Acuity (UCVA) of 20/32 or worse
- 6) Signed informed consent and HIPAA authorization or equivalent documentation necessary to comply with applicable privacy laws pertaining to medical treatment.
- 7) Willing and capable of complying with follow-up examinations for the duration of the study

7.2 EXCLUSION CRITERIA

- [REDACTED]

Exclusion Criteria [REDACTED] (all criteria apply to both eyes):

- 1) Concurrent use of systemic (including inhaled) medications that may impair healing, including but not limited to: antimetabolites, isotretinoin (Accutane[®]) within 6 months of treatment, and amiodarone hydrochloride (Cordarone[®]) within 12 months of treatment.

NOTE: The use of inhaled or systemic corticosteroids, whether chronic or acute, is deemed to adversely affect healing and subjects using such medications are specifically excluded from eligibility.

- 2) History of any of the following medical conditions, or any other condition that could affect wound healing: collagen vascular disease, autoimmune disease, immunodeficiency diseases, ocular herpes zoster or herpes simplex, endocrine disorders (including, but not limited to unstable thyroid disorders and diabetes), lupus, and rheumatoid arthritis.

NOTE: The presence of diabetes (either type 1 or 2), regardless of disease duration, severity, or control, will specifically exclude subjects from eligibility.

- 3) Subjects with a cardiac pacemaker, implanted defibrillator or other implanted electronic device.
- 4) History of prior intraocular or corneal surgery (including cataract extraction), active ophthalmic disease or abnormality (including, but not limited to, symptomatic blepharitis/conjunctivitis, recurrent corneal erosion, dry eye syndrome, neovascularization > 1 mm from limbus), retinal detachment/repair, clinically significant lens opacity, clinical evidence of trauma, corneal opacity within the central 9 mm and visible on topography, at risk for developing strabismus, or with evidence of glaucoma or propensity for narrow angle glaucoma.

NOTE: Subjects with open angle glaucoma, regardless of medication regimen or control, or an IOP greater than 21 mmHg at screening, are specifically excluded from eligibility.

- 5) Evidence of keratoconus, corneal dystrophy or irregularity, corneal edema, corneal lesion, hypotony, or abnormal topography.
- 6) Known sensitivity or inappropriate responsiveness to any of the medications used in the postoperative course.
- 7) A fellow eye that does not meet all inclusion criteria and does not fall within approved indications for treatment using excimer Laser.
- 8) Desire for monovision correction
- 9) Women who are pregnant, breast-feeding, or intend to become pregnant during the study.
- 10) Participation in any other clinical study, with the exception of a fellow eye treated in this protocol.

8. INVESTIGATOR SELECTION

8.1 INVESTIGATOR QUALIFICATIONS

JJSV will select ophthalmic surgeons who have completed a residency in ophthalmology (or its documented equivalent), are licensed to practice medicine and perform LASIK at his or her investigative site.

Investigators will be selected from surgeons who are experienced in using the IntraLase® keratome. All sites are required to have adequate staff support for reporting and subject follow-up, as well as the necessary instrumentation to conduct study testing. Each site will have one designated principal investigator; some sites may have additional surgical sub-investigators.

8.2 INVESTIGATOR OBLIGATIONS

Investigators are required to fulfill the following obligations:

- Conduct the study in accordance with the relevant and current protocol. Investigator will only make changes to a protocol after notifying and obtaining approval from JJSV and the Investigational Review Board (IRB) or Independent Ethics Committee (IEC), except when necessary to protect the safety, rights or welfare of subjects
- Personally conduct and supervise the study
- Maintain a list of appropriately qualified persons to whom the investigator has delegated significant trial-related duties
- Be responsible for protecting the rights, safety and welfare of subjects under the investigator's care and be responsible for the control and documentation of the devices under investigation
- Inform patients that the device(s) are being used for investigational purposes and that requirements relating to obtaining informed consent and IRB/IEC approval are met according to 21CFR50, 21CFR56, 21CFR812 and all other applicable laws and regulations
- Maintain confidentiality as required by HIPAA or similar laws and regulations
- Shall not obtain written informed consent from any subject to participate or allow any subject to participate before obtaining IRB/IEC approval and approval from the regulatory agency of the country in which the study is being conducted by the investigator
- Document in each subject's case history that informed consent was obtained prior to participation in the study as required by 21CFR812
- Report to JJSV and the reviewing IRB/IEC any adverse experiences that occur during the course of the study in accordance with applicable laws and regulations
- Maintain adequate and accurate records in accordance with applicable laws and regulations and make available all study documents and subject medical records for inspection by either JJSV, duly authorized regulatory agencies (e.g., FDA) and/or the IRB/IEC
- Submit progress reports on the investigation to JJSV and the reviewing IRB/IEC at regular intervals, but no less often than yearly as required by 21CFR812.150
- Report all changes in research activity and all unanticipated problems involving risks to patients to the IRB/IEC and JJSV
- Supervise and permit investigational device use and disposition in accordance with applicable regulations and protocol requirements. Upon completion of enrollment or termination of the study or the investigator's part of the study, or at JJSV's request, return to JJSV any remaining supply of the investigational device
- Provide sufficient accurate financial information to JJSV to allow JJSV to submit complete and accurate certification or disclosure statements as required by 21CFR54. Promptly update this information if any relevant changes occur during the course of the investigation or for up to one year following completion of the study
- Comply with all other obligations of clinical investigators and requirements according to all applicable FDA regulations (e.g., 21CFR812), all other applicable laws and regulations, and all conditions of approval imposed by the reviewing IRB/IEC, and the regulatory agency of the country in which the study is being conducted

- Ensure that all associates, colleagues and employees assisting in the conduct of the study are adequately informed about the protocol, the investigational device, their study-related duties and functions and agree to fulfill their obligations in meeting the above commitments.

Investigators shall provide adequate time and resources to conduct and report on the study. The Investigator, or delegate, shall notify JJSV of any change in the conduct of the study including changes in study personnel assigned to the study project, location of the investigational device(s), or maintenance of study records, etc.

8.3 INVESTIGATOR APPROVAL

It is the responsibility of the investigator to obtain prospective approval of the study protocol, protocol amendments or changes, informed consent forms and other relevant documents (e.g., advertisements) from the IRB/IEC as appropriate. All correspondence with the IRB/IEC should be retained in the Investigator Study Files/Notebook. Copies of IRB/IEC submissions and approvals should be forwarded to JJSV. Study sites will obtain IRB/IEC approvals and fulfill any other site-specific and/or region-specific regulatory requirements. The investigator is required to report to JJSV within five working days any withdrawal of approval by the reviewing IRB/IEC for his/her participation in the investigation.

Prior to the start of subject enrollment, the following documents must be signed and returned to JJSV:

- Confidentiality Agreement
- Clinical Trial Agreement
- Investigator Agreement/Protocol Signature page
- Clinical Investigator Brochure Signature page
- Financial Disclosure form
- Signed and dated copy of investigator's current curriculum vitae
- Copy of the investigator's current medical license (as available per country)
- Hospital/Ambulatory Surgery Center Clinical Study Acknowledgement, if required

By signing the study documents, the investigator agrees to conduct this study according to the obligations above and all other applicable regulatory and legal requirements.

9. EXPERIMENTAL PLAN

9.1 OVERVIEW

This study will be conducted in accordance with U.S. Code of Federal Regulations, the Declaration of Helsinki, ISO 14155 and all other applicable laws and regulations. The study will not begin until regulatory and IRB/IEC approvals have been obtained.

[REDACTED]

[REDACTED]

[REDACTED]

[REDACTED]

[REDACTED]

[REDACTED]

[REDACTED]

After signing the informed consent, subjects meeting all inclusion and none of the exclusion criteria [REDACTED] may be scheduled for surgery.

[REDACTED]

[REDACTED]

Although the study is not masked, to maintain consistency, it is recommended that a single individual (study technician or coordinator designated by the investigator) conduct all study-related vision testing, although a back-up person should also be designated and trained.

[REDACTED]

[REDACTED]

[figure not shown]
[REDACTED]

[REDACTED]

[REDACTED]

[REDACTED]

[REDACTED]

[figure not shown]

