5.2 OTHER ENDPOINTS

- [REDACTED]

- Optical Coherence Tomography (OCT) measurements – Anterior OCT scans will be taken pre- and post-surgery and measurements of the cornea and flap thickness will be recorded.
- BSCVA – Percent of eyes with a loss of >2 lines of best spectacle corrected visual acuity relative to preoperative acuity will be compared between the 2 eyes.
- UCVA – Percent of eyes with uncorrected visual acuity of 20/40, 20/32, 20/25, 20/20, and 20/16 or better will be compared between the 2 eyes.

- [REDACTED]
- [REDACTED]
- [REDACTED]
- [REDACTED]

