9.4 RANDOMIZATION

A randomization list will be created by an internal independent JJSV biostatistician for each investigative site. Subjects' eyes [REDACTED] will be randomized on a 1:1 basis between the study eye eye and the control eye. Randomization will take place after the subject has signed the informed consent document and has met all inclusion and exclusion criteria.

[figure not shown]
As part of the informed consent process, the investigator or delegate will explain to the subject the requirements of a randomized study and the differences expected between the study eye and the control eye.

[figure not shown]

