13. DOCUMENTATION

13.1 SOURCE DOCUMENTS

Source documents must be kept for all study subjects. Source documents may include a subject's medical records, hospital charts, clinic charts, the investigator's subject study files, as well as results of any diagnostic tests or procedures such as topographies or laboratory tests with photographs or instrument printouts.

Each site is expected to adhere to the clinic's own standard documentation requirements for medical charts/clinic notes. However, for the purposes of this clinical study, the medical charts/clinic notes must also include, at a minimum, the following data that will be considered source data and will be reviewed by JJSV:

- Subject's name and study identification number
- Subject's contact information
- Study protocol number and the Sponsor name (JJSV)
- A statement that informed consent was obtained prior to participation in the study (including the date)
- Dates of all subject visits and surgeries throughout the duration of the study
- Concurrent medications
- Corrected and uncorrected distance visual acuity (NOTE: ETDRS visual acuity score cards are considered source documentation and are to be retained by the site in the subject CRF notebooks)
- Manifest refraction
- Occurrence and status of any operative complications, postoperative medical findings and adverse events
- Occurrence and status of any subject complaints, e.g., ocular/visual symptoms
- The date the subject exited the study, and a notation as to whether the subject completed the study or reason for early exit.

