JJSV will also review source documents to verify that all required items have been documented in the subject medical charts. Refer to Section 14.1, Source Documents, for a list of items that are required for source documentation. In addition to subject files, study logs will be checked and conformance to lighting levels for visual acuity tests will be verified.

Training on study-specific procedures may also be conducted during monitoring visits.

Upon study completion, a final close-out site visit to each site will be made to monitor the last of the subject data records and finalize any outstanding study issues.

A separate Study Monitoring Plan will be established prior to study start that will define the type and frequency of monitoring visits and frequency of record monitoring.

MONITORING SCHEDULE (EXAMPLE IF NO SEPARATE STUDY MONITORING PLAN)

JJSV will visit each study site for site initiation visit to set up equipment and train all site staff on the study. JJSV will attend the first 1-month examinations at each study site. Interim monitoring visits will be conducted at least once a year or more often as needed according to subject exam compliance, clarity and consistency of data received by JJSV, resolution of data queries within the data management system, etc. JJSV will perform close out visits, and collect the equipment provided to the site to conduct the study.

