1 INTRODUCTION

This document summarizes the statistical methods to be implemented during the analysis of data for the evaluation of corneal flap creation using Cheetah femtosecond laser system and Cheetah patient interface. [REDACTED]

The investigators will use the Cheetah femtosecond laser, with the following possible procedures performed: 1) A comparison between the one piece PI (study eye) and two piece PI (control) with the Cheetah system in both eyes and/or 2) A comparison of commercial iFS femtosecond laser (IntraLase iFS) and PI (control) in one eye and the Cheetah femtosecond laser (with the one or two piece PI; study) on the other eye, both to create a LASIK flap on subjects' corneas.

| The eye to receive Cheetah flap will be randomized (ratio of 1:1 for right eye and left eye) and will be considered the study eye. Subjects █ will undergo refractive correction via corneal ablation on both eyes using a commercial excimer laser for vision correction (same excimer laser system will be used on both eyes).

The primary endpoint is the proportion of subjects with a score ≥ 3 in

stromal bed surface quality

Other endpoints include [REDACTED]
[REDACTED]
[REDACTED] anterior segment optical coherence tomography (OCT), [REDACTED]
[REDACTED] adverse events, [REDACTED]
[REDACTED]

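### The study is declared unmasked and no visible text keeps eye assignment from the vision tester: a modest, partly reducible risk of tester bias in the between-eye UCVA comparison, much smaller for BSCVA

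*Protocol*

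**What the plan says.** Protocol 9.1 states the masking status and the tester arrangement in one sentence: "Although the study is not masked, to maintain consistency, it is recommended that a single individual" should do all study vision testing. That person is a technician or coordinator chosen by the investigator, and a trained back-up is also named. The reason given is consistency.

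Protocol 5.2 lists two acuity endpoints under other endpoints:

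- UCVA: "Percent of eyes with uncorrected visual acuity of 20/40, 20/32, 20/25, 20/20, and 20/16 or better will be compared between the 2 eyes".
- BSCVA: "Percent of eyes with a loss of >2 lines of best spectacle corrected visual acuity relative to preoperative acuity", also compared between the two eyes.

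The visible controls on acuity testing are:

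- Protocol 13.1: "ETDRS visual acuity score cards are considered source documentation and are to be retained by the site in the subject CRF notebooks".
- Protocol 14.2: "conformance to lighting levels for visual acuity tests will be verified".
- SAP 1: the same excimer laser system is used on both eyes.

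The contrast is either the commercial laser against the Cheetah laser or, in the words of SAP 1, "A comparison between the one piece PI (study eye) and two piece PI (control) with the Cheetah system in both eyes". On timing, Protocol 9.4 says: "Randomization will take place after the subject has signed the informed consent document and has met all inclusion and exclusion criteria".

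**The concern.** Each subject supplies one study eye and one control eye, and the same person is meant to test both. A tester who knows which eye is which can encourage one eye harder, or accept a doubtful letter in one eye and not the other. Randomizing the eyes balances them before surgery but does not protect a measurement made afterwards. Using a single tester removes variation between testers, not the effect of that tester's knowledge.

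What is at stake is how a between-eye acuity result can be read. Whether the comparison shows a difference or none, a reader could not exclude tester expectation as a contributor.

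**Working it through.** The plan gives no figure to reproduce here, and the point rests on no power or sample size calculation. The check is a comparison of the texts, plus one line of arithmetic for scale.

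**1. Is the tester unaware of assignment?** Protocol 9.1 says the study is not masked and makes no visible exception for the tester named in the same sentence. Nothing visible in Protocol 9.4, 13.1 or 14, or in the SAP, restricts who sees the assignment. Protocol 9.1 allows the tester to be the coordinator. Protocol 13.1 requires acuity and operative complications in the same chart notes, and Protocol 14.2 provides a site log of patient interface use. The tester could learn the assignment from such records, but the documents do not show that this happens.

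**2. Do the visible controls conceal assignment?** Retained score cards document what was recorded, not how each eye was prompted. Lighting checks and a common excimer system equalise conditions. All three limit or document discretion; none hides which eye is which.

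**3. Which measurements are exposed?** Randomization follows confirmed eligibility, so preoperative acuity, including the BSCVA baseline, is measured before assignment exists. Only postoperative testing is at issue.

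**4. Are the two endpoints equally exposed?** No.

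- UCVA is cut at five levels. An eye close to any of them can change category on a small difference in letters read.
- BSCVA counts only a loss of more than 2 lines. Protocol 10.1 equates 2 lines with 10 ETDRS letters. A tester would have to shift an unchanged eye by more than 10 letters, or the eye's true loss would already have to lie near that limit.

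**5. Scale.** Protocol 2 (synopsis) sets a minimum of 40 eyes with optimized settings and allows up to 300 subjects. Assuming one study eye per subject, one eye placed on the wrong side of a UCVA cut-off moves that group's percentage by:

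- 1/40 = 0.025, or 2.5 percentage points, with 40 eyes;
- 1/300 = 0.0033, or 0.33 percentage points, with 300 eyes.

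This is the weight of one eye, not an estimate of bias. The documents give no acuity distribution, test-retest variability or tester effect, so the number of eyes that might cross cannot be estimated.

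**The case against.** **The gap may come from redaction.** Much of Protocol 9.1 is blacked out, including lines directly after the quoted sentence, and sections 9.2, 9.6 and 9.7 cannot be read. Monitors verify lighting levels although no level is visible, so some acuity procedures evidently sit in unseen text. This stands as a limit. The explicit not-masked statement beside the tester instruction makes a hidden tester provision less likely but does not rule one out.

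**It is an openly stated choice on minor endpoints.** UCVA and BSCVA are not primary, no visible test, margin or success rule attaches to them, and the existing controls narrow scoring discretion. This also stands, and it keeps the point small. It does not answer the point, since disclosing an unmasked design does not remove the bias it allows.

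**The consent discussion might seem to strengthen the concern.** Protocol 9.4 has the investigator explain "the differences expected between the study eye and the control eye", and a reader might infer that subjects learn their assignment and pass it to the tester. The text does not support this. The explanation belongs to consent, and randomization comes after consent is signed, so no eye has been assigned at that moment. The visible text does not say whether subjects learn later which eye is which.

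**The stated hypothesis might seem to give the bias a direction.** Protocol section 2 expects the study eye to be at least as good, but it speaks of flap quality, not acuity. It does not settle which way a tester would lean.

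**Conclusion.** The point holds as a minor suggestion. The study is declared unmasked, no visible text withholds eye assignment from the designated tester, and the between-eye UCVA thresholds therefore carry a modest risk of tester bias of unknown size and direction. The BSCVA comparison carries the same kind of risk to a much smaller degree. The risk is partly reducible, not fully avoidable, because masking the tester does not mask a subject who knows the assignment.

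This rests on the visible text. If a redacted or unreadable section already keeps the tester unaware, all that remains is to qualify the not-masked sentence.

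A reader might go further and conclude that the acuity results are biased, or that the trial's main conclusion is affected. The documents support neither: they show an opportunity for bias, not its occurrence. The primary stromal bed score is a separate matter, graded relative to the control eye through an investigator questionnaire. This point neither addresses nor clears it.

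**What to change.** Amend Protocol 9.1 so that, at postoperative visits, the already designated tester and back-up:

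- are not told which eye received which laser or patient interface;
- have no access to the randomization list, operative forms or patient interface log before acuity is recorded;
- record acuity on forms labelled OD/OS only.

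Subjects should be asked not to disclose to the tester which eye received which device. Where a site cannot do this with existing staff, it should record that, and its acuity comparison should be reported as unmasked. If a tester-level provision already exists, qualify the not-masked sentence instead.

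The cost is protocol wording, delegation entries and a short addition to the training already foreseen in Protocol 14.1 and 14.2, at up to 5 sites. No examination or staff member is added. The downside is some separation of roles and records: a coordinator who tests vision should not also handle randomization or operative forms, and acuity must be recorded apart from operative notes that share the chart. Protocol 8.1 describes staffing only as adequate, so some sites may need the fallback. Subjects who know their assignment remain unmasked.
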